NCT03781323

**Neoadjuvant FOLFOX therapy with Short Course Radiation and active surveillance in locally advanced
Rectal Cancer: A Phase II Study**

Version Date: 12/9/2019

Principal Investigator: [name]

Statistician: [name]

**Site: University of Rochester
James P. Wilmot Cancer Institute
[name]
[name]**

Figure 1. Schema

- Total number of patients enrolled to start chemotherapy, N=30
- All patients included in evaluation of complete clinical response, safety, toxicity, quality of life, and overall survival

[figure not shown]

Table of Contents

- 1.0 Purpose of Study and Rationale
 - 1.1 Purpose of Study
 - 1.2 Rationale
- 2.0 Study Objectives
 - 2.1 Primary Objective
 - 2.2 Secondary Objectives
- 3.0 Study Design
- 4.0 Selection Criteria
 - 4.1 Inclusion Criteria
 - 4.2 Exclusion Criteria
- 5.0 Methods and Study Procedures
 - 5.1 Subject Recruitment and Consent
 - 5.2 Pretreatment Evaluation
 - 5.3 Administration Schedule
 - 5.4 Disease Progression
 - 5.5 Posttreatment evaluation
 - 5.6 Discontinuation of Study
- 6.0 Schedule of Events
- 7.0 Treatment Dosing Modifications
- 8.0 Study Treatment Toxicities
 - 8.1 Oxaliplatin
 - 8.2 Leucovorin
 - 8.3 5-Flurouracil
- 9.0 Adverse Events Monitoring and Reporting
 - 9.1 Definition of Adverse Event
 - 9.2 Definition of Serious Adverse Event
 - 9.3 Reporting of Adverse Events
 - 9.4 Severity of Adverse Events
- 10.0 Objectives and Data Analysis
 - 10.1 Primary Endpoint
 - 10.2 Secondary Endpoints
 - 10.3 Data Analysis
- 11.0 Data Safety and Monitoring
- 12.0 Data Confidentiality and Storage
- 13.0 Data and Specimen Banking for Future Use
- 14.0 References

1.0 Purpose of Study and Rationale

1.1 Purpose of Study

The purpose of this study is to evaluate the treatment of patients with locally advanced rectal cancer for complete response to neoadjuvant chemotherapy followed by short course radiation without surgery. These patients will be evaluated for complete clinical response (cCR) after completing up to 12 cycles of modified FOLFOX (mFOLFOX) (fluorouracil, leucovorin, oxaliplatin) chemotherapy, plus the use of short course radiation. Patients who have stable or progressive disease will be removed from study and treated per discretion of the treating physician. Those determined to have a near complete or complete response will complete full neoadjuvant treatment (chemotherapy and short course radiation) and undergo close surveillance with watchful waiting for local recurrence without immediate surgery. The primary endpoint of this study will be the rate of cCR, which is to include complete and near complete clinical response with induction chemotherapy and short course radiation, with secondary endpoints of disease-free survival (DFS), overall survival (OS), quality of life (QOL), as well as evaluation of safety and toxicity.

1.2 Rationale

Colorectal cancer has been well studied as it is the second leading cause of cancer death in the United States, with over 39,000 estimated newly diagnosed cases of rectal cancer each year. Due to ongoing improvements in treatment, there has been a decline in the overall incidence and mortality in the past two decades though annual deaths still total approximately 49,000 from combined colorectal cancer[1]. The current standard of care for locally advanced rectal adenocarcinoma is chemoradiation therapy (CRT) before or following surgical intervention, which has yielded a significant decrease in local recurrence at the expense of acute or extended toxicity from treatment. Disease free survival for neoadjuvant or adjuvant treatment for locally advanced rectal cancer has been shown to be 68% and 65% at five years, respectively[2].

However, this multi-modality treatment of CRT followed by surgery is associated with a high potential for creating substantial morbidity including diarrhea, hematologic toxicity, dermatologic toxicity, sexual dysfunction, bowel and bladder dysfunction, small bowel obstruction, and strictures at the site of anastomosis[2-4]. Additionally, patients undergoing surgery have higher rates of wound dehiscence following CRT[4]. Though sphincter-sparing surgery is preferable for improved quality of life, it is not always possible to obtain negative margins. When sphincter-sparing surgery is not an option, such patients require an abdominoperineal resection (APR), resulting in a permanent colostomy.

In review of earlier studies employing CRT, much of the current evidence supporting neoadjuvant therapy is derived from the randomized controlled trial by the German Rectal Cancer Study Group in 2004 comparing preoperative CRT with postoperative treatment. Though rates in overall survival remained unchanged, local recurrence rates were decreased, and more patients completed preoperative treatment. We note that 8% of those patients in the preoperative CRT arm were found to have a complete pathologic response (pCR) based on histopathology at the time of surgery[2].

Due to treatment related morbidity, and a growing trend of rectal cancer in patients younger than 50 years old, it has come in to question if rectal cancer has been over-treated in select

individuals[1]. At our own institution, following patient enrollment evaluating total neoadjuvant therapy (TNT) with 6 cycles of FOLFOX therapy followed by surgery in a collaborative study, it was noted that several individuals had a clinical complete or near complete response, or complete pathologic response. We now seek to evaluate if total neoadjuvant therapy with chemotherapy alone may produce such a response in some individuals, utilizing chemotherapy with short course radiation therapy. Those with a complete or near complete response may be spared surgical intervention.

Neoadjuvant therapy with watch and wait surveillance

In a 2014 study, 90 of 183 (49%) patients in a single institution study achieved a complete clinical response (cCR) after receiving CRT for 8 weeks alone. Following a close surveillance schedule of visits, 28 (31%) of initial responders experienced local recurrence, with 17 of these patients within the first year. Salvage therapy with surgery was feasible in 26 (93%) of these patients, and R0 resection in 25 (89%). The results of this study suggest that there is a population of patients not requiring CRT with surgery for their locally advanced disease. With a median follow up of 60 months, 62 (34%) of the 183 patients remained disease free and could safely avoid surgery. The 5-year overall survival for all patients was 91% and disease-free survival 68%. This study included tumors cT2-T4 and node-positive disease[4].

Evaluation of pathologic complete response rate after chemotherapy, chemoradiation

Several more recently published studies evaluated tumor response to neoadjuvant chemotherapy alone followed by surgery. Schrag et al. in 2014 conducted a phase II, single institution study of 32 patients with T2N+, T3N0, or T3N+ rectal tumors, excluding T4 staged disease. Patients underwent six cycles of FOLFOX plus bevacizumab, followed by total mesorectal excision (TME). Following completion of neoadjuvant therapy, 8 patients (25%) were found to have pCR at surgery. Four-year DFS and OS were 84% and 91%, respectively[5]. One may hypothesize the increased rates of DFS and OS may be improved from earlier trials with the exclusion of T4 tumors as part of the study. In a similar pilot study of 45 patients who had undergone six cycles of neoadjuvant FOLFOX without bevacizumab, only 2 patients (4.4%) were found to have cCR, with 29 (64.4%) in partial response, however, pCR following TME was observed in 8 (17.8%) patients. This study had included T4a disease (T2-T4a, N0-N2) and three-year DFS 67.9% and OS 80.8% [3].

Initial results of the Chinese FOWARC study, a multicenter trial of 495 patients comparing neoadjuvant fluorouracil-radiotherapy, FOLFOX-radiotherapy, and FOLFOX alone, achieved pCR in 14.0%, 27.5%, and 6.6% of patients, respectively. However, study protocol allowed for a minimum of only four cycles of FOLFOX therapy preoperatively, and inclusion criteria allowed for stage II (T3-4, N0) or stage III (T1-4, N1-2)[6]. The above study found lower rates of pCR with chemotherapy alone, especially when cycles became increasingly limited.

Complete response rates following neoadjuvant therapy with combined chemotherapy and chemoradiation.

There are a number of studies that has specifically evaluated pathologic or clinical complete response following the combination of CRT followed by further consolidative chemotherapy. Habr-Gama et al. evaluated 34 patients with CRT followed by 3 additional cycles of 5-FU and leucovorin, no oxaliplatin, followed by surveillance if there was complete response. CCR was maintained for at least 12 months in 48% of patients, with 5 additional patients demonstrating pCR after surgery, with portal combined complete response rate of 65%. This study did evaluate for long-term durability of results. A multicenter phase II study by Garcia-Aguilar et al. involving 292 patients compared pCR in patients receiving standard neoadjuvant CRT, or followed by 2, 4, or 6 cycles of FOLFOX. The study included patients with stage II-III locally advanced rectal cancer. The standard neoadjuvant group obtained a pCR rate of 18%, with pCR rates of 25%, 30%, and 30% with increasing cycles of FOLFOX therapy, respectively.

Recently, a retrospective cohort has been published by Memorial Sloan Kettering Cancer Center evaluating 628 patients with locally advanced T3-4, or N1-2 rectal cancer evaluating patients who had either received TNT or chemoradiation followed by adjuvant therapy after surgery. Participants in TNT cohort received 8 cycles of FOLFOX or 5 cycles CAPOX, followed by chemoradiation with 5-FU or capecitabine plus long course radiotherapy. The possibility of pCR was explained to patients who were found to have cCR at completion of TNT and given the choice if to proceed to surgery or undergo watchful waiting. CCR was recorded only at the 12-month mark, as most local recurrences occurred within that period. Of 308 patients with stage II or III disease, 18.3% of patients had a sustained cCR, and 21.8% with pCR with those who had proceeded immediately to surgery. A total of 36% of patients had either pCR or cCR with TNT at one year, compared to 21% of patients with pCR who received neoadjuvant CRT followed by adjuvant therapy. [7]

Short Course radiation in treatment of rectal cancer

In the above studies, we see that total neoadjuvant therapy has not been studied with chemotherapy and radiation and watch and wait surveillance, and with chemotherapy alone preceding surgery. The addition of radiation to locally advanced rectal tumors may provide additional local control and downstaging tumors prior to surgery. As there is growing evidence of it's not inferiorly to long course radiation in reducing patient time of treatment, our trial will add short course radiation to neoadjuvant chemotherapy.

Short course radiation therapy (RT) 5 to a radiation therapy inferior fractions, typically within one week compared to 5-6 weeks with long course RT. Short course RT has been studied in phase II and subsequently phase III trials by Bujko et al. in which it was compared with long course RT. Results of a phase III study demonstrated T3 and T4 tumor undergoing short course RT have significantly lower overall toxicity ($p=0.006$), overall survival of 73% versus 65% at 3 years (0.046) and trended towards improved pathologic response (0.07). The Stockholm III that he compared long course RT with a delay prior to surgery, short course RT with delay, and short course RT without delay. Short course RT with delay demonstrated similar outcomes for recurrence free survival and multivitamin analysis compared to the 2 other cohort, but demonstrated significantly lower postoperative complications and short course RT without delay.

Since completion of these studies, short course RT has been included in TNT trials. In a recently published abstract of a retrospective cohort study, 388 patients received either a long course RT (n=236) or short course RT (n=152) as part of TNT prior to surgery. Though the short course cohort had a higher number participants with more advanced stage disease, pCR and recurrence rates were found to be not severely different from the long course cohort, further support that short course RT is not inferior to long course therapy. Prospective trials are currently underway; the RAPIDO trial, early active but no longer enrolling patients, is evaluating the use of short course RT with chemotherapy prior to surgery (TNT) compared to conventional long course chemoradiation followed by adjuvant therapy postoperatively.

To our knowledge, there are no studies currently evaluating a complete response to full, upfront neoadjuvant chemotherapy with mFOLFOX plus short course CT in locally advanced rectal adenocarcinoma followed by surveillance. From review of available literature, we conclude that there is the potential for an identifiable population of patients that may benefit from treatment with systemic therapy and short course RT with a complete or near complete response, while sparing these patients the toxicity of a total mesorectal excision. Earlier phase II studies demonstrate a range of complete response from 25% to 65% for total neoadjuvant therapy, but we conclude from these studies that the complete response rate is likely in the range of 30-40%.

In conclusion, we hypothesize that some patients with locally advanced rectal cancer with stage I (T2N)-IIIB disease (excluding clinical T4 or N2b staging) will benefit from our proposed protocol of total neoadjuvant therapy, with proposed reduction in surgical related toxicities.

2.0 Study Objectives

2.1 Primary Objective

The primary objective of this study will be to assess the rate of clinical complete or near complete response to total neoadjuvant therapy with up to 12 cycles of mFOLFOX and short course radiation.

2.2 Secondary Objectives

The secondary objectives of this study will be to evaluate rate of clinical complete response to induction chemotherapy, 1-year disease free survival, 5-year disease free survival, overall survival, quality of life assessment, as well as safety and toxicity of treatment. Patients proceeding to surgery after stable or progressive disease during total neoadjuvant treatment and patients with recurrence within 5 years will be evaluated for rate of R0 resection.

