3.0 Study Design

This is a multi-center, phase II study investigating the efficacy of total neoadjuvant therapy with mFOLFOX and short course radiation and selective non-operative management in patients with locally advanced rectal cancer.

Participants with Stage IIA, IIIA, IIIB rectal adenocarcinomas, except for any T4 or N2b disease, who would otherwise undergo long course concurrent chemotherapy and radiation therapy followed by TME may be enrolled for treatment with mFOLFOX therapy. Participants with lower sphincter rectal cancer deemed not eligible for sphincter sparing surgery are not eligible for participation. Participants would be treated with up to 12 cycles of mFOLFOX therapy. (One cycle of mFOLFOX= 14 days) and short course radiation.

All patients will be evaluated once following six cycles of chemotherapy via endoscopy and CT plus MRI.

Patients with a partial, near or complete response will receive an additional 4-6 cycles of chemotherapy followed by reassessment.

Patients with stable or progressive disease defined as less than 20% reduction will be removed from study.

Following completion of all chemotherapy (10-12 cycles) patients will be re-assessed via endoscopy and CT plus MRI. Patients will then receive short course radiation followed by repeat assessment with endoscopy and CT/MRI. Those patients with evidence of complete or near complete clinical response following completion of all chemotherapy and radiation will be treated non-operatively and undergo close surveillance.

Patients with a partial response or stable disease will undergo TME.

Those with <20% response will be removed from study and undergo treatment per the treating investigator. These patients will be followed for survival at six month intervals for up to 5 years.

All patients will be followed for 5 years following last date of treatment:

- For patients in the study not requiring surgery following chemotherapy, the last day of treatment will be considered the last day of mFOLFOX therapy.
- For patients who receive short course radiation, the last day of treatment will be considered the last day of radiation.
- For patients in the TME group, the last day of treatment will be considered the day of surgery.

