5.2 Pre-treatment Evaluation

Patients eligible for treatment and have been consented will be registered in RED CAP by the Study Coordinator. Those patients who have been consented and become participants in the trial must complete pretreatment evaluation within 45 days (+/- 15 days) days of starting neoadjuvant therapy administration (Cycle 1, Day 1).

All patients will undergo pre-treatment staging via physical examination, labs, proctoscopy/sigmoidoscopy, baseline imaging, and pathologic assessment of the tumor within 45 days from the start of treatment (+/-15 days). Colorectal surgery must document if the participant has a lower rectal adenocarcinoma, generally tumors in the lower third of the rectum, not eligible for sphincter sparing surgery.

Pelvic MRI will also be performed to obtain baseline evaluation of the tumor. Endorectal ultrasound may be used if MRI is not conclusive in lymph node evaluation. Each patient will be evaluated by the treating physician to determine their eligibility for mFOLFOX therapy. If a patient is unable to obtain a CT due to contrast allergy or other contraindication, MRI imaging will be acceptable for evaluation.

Patients will complete an evaluation prior to treatment regarding their quality of life (QOL). This will also be completed during the interval assessment, restaging assessment, post radiation assessment, 6 months follow up, and annually for 5 years. Validated QOL forms EORTC QLQ-30, and EORTC QLQ-CR29 will be used for assessment[8, 9]. These two surveys can be completed on the phone or at clinic visits, and consist of four pages of questions pertaining to daily activities, symptoms, and overall health before, during, and after treatment. These would take an estimated 10 minutes to complete.

Rescreening may be allowed one time within 30 days of a screen failure. The patient will retain the same screening number.

Optional blood work will also be collected for correlative biomarkers at baseline, at cycle 6 day 1 and at the time of the post radiation assessment.

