5.6 Discontinuation of Study

Participants may be discontinued from treatment for any of the following reasons:

1. The participant wishes to no longer participate in treatment
2. The provider in charge of the patient’s treatment withdraws the participant

3. The participant is determined to have unacceptable or intolerable toxicity
4. A participant becomes pregnant
5. A participant is diagnosed with another malignancy requiring treatment
6. The participant is lost to follow up
7. If treatment is held for greater than 28 days

All participants who are discharged from treatment and the study will continue to be followed for severe adverse events, disease free and overall survival whenever possible.

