10.3 Data Analysis

We aim to accrue 40 participants over approximately a 5-year period. Though we hypothesize that this study will be of clinical benefit to those who may avoid surgical intervention, we have no knowledge that a similar study has been conducted. Thus, we aim to gain a preliminary estimate of the rate of locally advanced rectal cancer patients that can be spared surgical intervention through the use of neoadjuvant chemotherapy plus short course radiation. We anticipate a 30% rate of complete or near complete clinical response to neoadjuvant chemotherapy plus short course radiation at the post-radiation assessment. This rate will include subjects discontinuing mFOLFOX due to stable or progressive disease at the interval assessment or re-staging assessment in the denominator.

With an anticipated response rate of 30%, a sample size of 40 subjects produces a one-sided 95% lower-limit exact binomial confidence interval with a width of 13.4% (lower limit of 16.6%). The maximum width of a one-sided 95% lower-limit confidence interval with 40 subjects would be 16.1% when the response rate is 50%. We target the lower limit of the confidence interval to determine if this regimen demonstrates sufficient evidence of efficacy to be considered worthy of future study.

The complete or near complete response rate and associated 95% one-sided exact binomial confidence interval will be presented. Disease-free and overall survival will be described using the Kaplan-Meier method. Types and grades of adverse events will be tabulated. Changes in QOL (from baseline) will be described using means and standard deviations at each time point assessed. We will calculate these summary measures separately in those who obtain a complete or near complete response to up to 12 cycles of mFOLFOX and short course radiation and are entering watch and wait surveillance, and those who required surgery with or without radiation therapy prior to completion of mFOLFOX therapy. QOL will be measured using validated

QOL forms EORTC QLQ-30, and EORTC QLQ-CR29 as mentioned in Section 5.2, with paper-based surveys and scored according to the EORTC scoring manual [10].

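### The R0 objective covers patients who are removed from study with no provision for margin status, their later QOL collection is stated inconsistently, and the 10.3 surgery group omits on-study TME patients

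*Combined protocol and SAP*

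**What the plan says.** **R0.** Section 2.2 makes the rate of R0 resection an objective for "Patients proceeding to surgery after stable or progressive disease during total neoadjuvant treatment", and for patients whose disease recurs within 5 years. Neither 10.2 nor 10.3 mentions R0.

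**Removal and follow-up.** Section 3.0 says "Patients with stable or progressive disease defined as less than 20% reduction will be removed from study". Section 5.4 repeats this for the interval assessment. Later in 3.0, those with less than 20% response leave the study for treatment chosen by the investigator, and "These patients will be followed for survival at six month intervals for up to 5 years". Table 2 footnote e also gives removal followed by survival follow-up. Section 5.6 is wider: participants discharged from treatment and study "will continue to be followed for severe adverse events, disease free and overall survival whenever possible". A separate sentence in 3.0 sends patients with partial response or stable disease after radiation to TME, and 3.0 gives the TME group five years of follow-up.

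**QOL.** Section 5.2 schedules QOL before treatment, then "This will also be completed during the interval assessment", at restaging, after radiation, at 6 months and yearly for 5 years, by phone or in clinic. Table 3 footnote a extends QOL to everyone, expressly including patients who stopped after cycle 6 for stable or progressive disease. Table 4 footnote a does the same for those who went to surgery. The schema has "All patients included in evaluation of complete clinical response, safety, toxicity, quality of life, and overall survival".

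**QOL analysis.** Section 10.3 summarises QOL change in two groups: complete or near complete responders entering watch and wait, and "those who required surgery with or without radiation therapy prior to completion of mFOLFOX therapy".

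**The concern.** An objective needs a population, a measurement and an analysis. For R0, 2.2 supplies the population and nothing else in the plan supplies the other two. Much of that population is made up of patients whom the plan removes and who are then treated at the investigator's choice, in a study that 3.0 calls multi-center. Retrieval of their pathology reports cannot be taken for granted.

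For QOL, a coordinator who reads 3.0 and Table 2 could reasonably stop the questionnaires at removal, while one who reads the Table 3 footnote would continue. Sites may differ, and QOL not collected at the time cannot be recovered.

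At stake is whether the trial can say how surgery went for patients in whom the strategy failed, and how their quality of life compares descriptively with that of patients spared surgery. The primary endpoint is not affected: 10.3 keeps patients who stop at the interval or restaging assessment in the denominator.

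**Working it through.** No figure in the plan can be reproduced on this point, so the check sets the passages side by side.

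**Step 1. Who is in the R0 set, and is margin status collected?**

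| Patients | Follow-up stated | Margin status collected? |
|---|---|---|
| Removed at the interval assessment (3.0, 5.4, Table 2 footnote e) | Survival; 5.6 adds severe AEs and DFS where possible | Not stated |
| Stable disease after radiation, sent to TME (3.0) | Five years, TME group | Not stated |
| Recurrence within 5 years during watch and wait | Table 4 | Not stated |

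Tables 2 to 4 have no operative or pathology item. Section 5.5 describes post-surgery follow-up only for patients operated on after partial response, and the items it lists are history and examination, CEA, imaging and colonoscopy. So margin status is not provided for in any row, and the first row has the thinnest follow-up. Partial responders who have TME are not in the 2.2 set as worded, unless they recur.

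**Step 2. Is the route for stable disease consistent?** Section 10.1 defines stable disease as a decrease below 20%. After radiation, 3.0 sends stable disease to TME and also removes those with less than 20% response. The same patient can meet both statements, and with them two follow-up paths. These sentences must be reconciled; no clinical rule is suggested here.

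**Step 3. Which QOL is in doubt for removed patients?**
- Baseline and interval assessment: collected, because removal is decided at the interval assessment.
- Restaging: Table 3 times it 4 to 12 weeks after the last chemotherapy. A patient stopped after cycle 6 has such a date, so the visit can be placed, although the title of Table 3 limits it to responders.
- Post-radiation: timed 6 to 12 weeks after radiation, so there is no anchor without radiation.
- Six months and yearly (5.2): calendar visits that could continue. The Table 3 footnote supports this; 3.0 and Table 2 footnote e do not mention it.

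Only QOL after the interval visit is in doubt.

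**Step 4. Do the two 10.3 groups cover the patients?** Under 3.0, TME for partial response on study follows all chemotherapy (10 to 12 cycles) and radiation. Such a patient is not a complete or near complete responder, so is not in the first group. Surgery came after mFOLFOX was completed, so the patient is not in the second group either.

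**Step 5. How many might be removed? (illustration only)** The FOLFOX pilot of 45 patients cited in 1.2 reports 2 complete and 29 partial clinical responses after six cycles: 45 − 2 − 29 = 14, and 14/45 = 31.1%. With 40 patients (10.3), 0.311 × 40 = 12.4; with the 30 in the schema, 0.311 × 30 = 9.3. At an assumed 10%, the counts are 4 and 3. These are patients removed; the number then operated on is unknown and can only be smaller or equal.

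**The case against.** The other side is strongest on QOL. A reader might infer that removed patients contribute no QOL data. The documents do not support that. Two assessments precede removal, so a change from baseline exists for each patient who completes both. Table 3 footnote a names exactly this group, and 5.2 has calendar visits. A site that dropped QOL would be acting against an explicit footnote. This stands, and leaves only a conflict between passages.

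A reader might also infer that removed patients are followed for survival and nothing else. The word only does not appear in 3.0, and 5.6 adds severe adverse events and disease-free survival. This also stands, but 5.6 does not reach margin status.

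On R0, the set also includes recurrences and, by one sentence of 3.0, stable-disease patients who stay in follow-up, and margins may be obtainable from charts. So the R0 rate need not be empty. But no passage requires retrieval, and a rate built from whoever remains on study answers a narrower question than 2.2 asks.

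On the 10.3 group, the time limit could be attached to radiation alone, so that the group becomes everyone who had surgery. That reading is possible, but under 3.0 nobody on study receives radiation before chemotherapy is complete, so the qualifier would then do little work. The ambiguity itself needs removing.

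Finally, a reader might infer a definite bias in the QOL comparison, in points on the scale. The documents give neither the share removed nor their QOL difference. The pilot used its own criteria and included T4a disease, and 10.3 plans only descriptive means and standard deviations. No such figure can be supported.

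**Conclusion.** The concern holds in three limited parts.

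1. The R0 objective in 2.2 has no data item and no analysis. Followed as written, the rate would either lack the removed patients or rest on those still on study.
2. Sections of the plan conflict on whether QOL continues after removal. The doubt is confined to assessments after the interval visit.
3. As most naturally read, the 10.3 surgery group leaves out on-study patients who have TME after completing chemotherapy and radiation; they fall in neither summary.

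These are secondary, descriptive outcomes, so the point is worth correcting but does not threaten the main result. The size is not derivable from the documents. The range of about 4 to 12 of 40 (3 to 9 of 30) assumes that 10% to 31% are removed, and the upper end borrows a pilot with different eligibility. The three parts do not depend on that range.

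**What to change.** - **Reconcile** 3.0 (including its two statements on stable disease), Table 2 footnote e and Table 3 footnote a. The sponsor should settle the clinical rule; this review proposes none.
- **After removal** for stable or progressive disease, state that patients continue the 5.2 QOL schedule, by phone if needed, and say how visits without a treatment anchor are timed. At the six-monthly contacts already planned, record the date, type and margin status of any rectal resection.
- **In 10.2 and 10.3**, add R0 as an endpoint with its denominator and summary, and say whether TME after partial response is included.
- **In 10.3**, define the surgery QOL group as all patients having rectal resection, reported separately for those removed early and those having TME after radiation.

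The cost is protocol wording, one operative and pathology report per operated patient, and a questionnaire that 5.2 puts at about 10 minutes. The downside is that some removed patients will decline or be treated elsewhere, so QOL will be incomplete. The number with data out of the number expected should be reported at each time point, and likewise for margin status.
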